9.9.4 Analysis of Secondary Safety Variables

Summary statistics (mean, median, sample size, standard deviation, minimum, and maximum) will be computed on the raw and change from baseline values for each vital sign parameter by time point, for each tumor type and overall. The pre-injection time point will serve as baseline. If there are multiple vital signs taken at any time point, then the latest set of vital signs will be used for the analysis. All vital sign data will be listed.

Summary statistics (mean, median, sample size, standard deviation, minimum, and maximum) will be computed on the raw and change from baseline values for each quantitative laboratory parameter by time point, for each tumor type and overall. The screening time point will serve as baseline. If there are multiple labs taken at any time point, then the latest set of labs will be used for the analysis. All clinical laboratory data, including any qualitative urinalysis results, will be listed.

Summary statistics (mean, median, sample size, standard deviation, minimum, and maximum) will be computed on the raw and change from baseline values for each ECG parameter by time point, for each tumor type and overall. The screening time point will serve as baseline. If there are multiple ECGs taken at any time point, then the latest set of ECGs will be used for the analysis. All ECG data will be listed.

Additional analyses of safety variables for this study may be conducted as described in the Statistical Analysis Plan document.

9.9.5 Analysis of Primary Diagnostic Variables

The localization rate, defined as the proportion of ITT subjects that had at least one lymph node identified intraoperatively, along with a 95% confidence interval will be computed for Lymphoseek for each tumor type and overall.

The average number of lymph nodes identified intraoperatively by Lymphoseek per subject, along with a 95% confidence interval, will be computed for each tumor type and overall.

The proportion of ITT subjects who had preoperative SPECT performed will be summarized by tumor type and overall. The proportion of patients who had a hot spot on the scan will also be summarized by tumor type and overall. For those patients with a hot spot, the time from Lymphoseek injection to hot spot localization will be summarized.

The average number of lymph nodes identified with preoperative SPECT per subject, along with a 95% confidence interval, will be computed for Lymphoseek by tumor type and overall.

The average difference in the number of lymph nodes identified with preoperative SPECT per subject and the number of lymph nodes identified intraoperatively per subject, along with a 95% confidence interval, will also be computed.

The nodal and subject agreement of central pathology assessment to local pathology assessment will be computed as follows:

	Lymph nodes whose local and central pathology assessments were either	
Nodal	both positive or both negative	
Agreement =	Lymph nodes with non-missing local and central pathology results	

Where agreement on the subject level means that a subject either has at least one pathologypositive node with local and central pathology or has all pathology-negative nodes with local and central pathology. For the analysis of nodal agreement and subject agreement, only nodes that have non-missing local and central pathology results will be considered. Along with the agreement proportions, a 95% confidence interval will be computed for each endpoint. Subgroup analyses by tumor type will also be performed within the ITT and PP analysis populations.

The nodal false negative rate will be computed for Lymphoseek as the number of pathologypositive lymph nodes that were missed intraoperatively by the tracer divided by the total number of pathology-positive lymph nodes. A 95% confidence interval will also be computed. False negative rates also will be calculated separately for the blinded central pathology assessment and the local pathology assessment.

The nodal sensitivity will be computed for Lymphoseek as the number of pathology-positive lymph nodes identified intraoperatively by the tracer divided by the total number of pathology-positive lymph nodes. A 95% confidence interval will also be computed. Sensitivities also will be calculated separately for the blinded central pathology assessment and the local pathology assessment.

The number and proportion of subjects upstaged by Lymphoseek will be computed along with a 95% confidence interval, where upstaging by an individual tracer is defined as a subject who had at least one pathology-positive node identified by one tracer and no pathology-positive nodes identified by the other tracer.

The change in subject nodal staging will be assessed via shift tables. A shift table for Lymphoseek will be produced to show the number of subjects with each combination of presurgery and post-surgery nodal staging. Each subject's post-surgery staging will be based on the pathology results of those nodes identified by Lymphoseek. For the purposes of this analysis, a subject may have two different post-surgery nodal staging results, one based on Lymphoseek-identified nodes and the other based on Lymphazurin-identified nodes (see Section 9.9.6).

Changes in treatment plan and relation to lymph nodes identified by Lymphoseek will be listed.

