	institutional imaging protocol time of injection when po STATIC planar imaging sho minutes post injection. At least 15 minutes and r Lymphoseek injection, subjection	s. Imaging should begin at the erforming dynamic imaging. ould begin approximately 15 no more than 8 hours after ects will undergo surgery to	
	remove the primary tumor a during the lymphatic mappin with institutional practice, Lyn in the operating room immedi The injection of Lymphazur deemed appropriate by the su the standard of care at the samples will be collected for s surgery.	and all lymph nodes detected ag procedure. If in agreement mphazurin will be administered ately before or during surgery. in will only be performed as argeon and in accordance with clinical site. Blood and urine safety laboratory analyses post-	
	Safety follow-up (Day 4 to physical examination, and re performed between 4 to 14 da Postsurgical treatment plan; t (TNM) staging; and clinical gr	• 14): Vital sign assessment, eview of medications will be ys after Lymphoseek injection. tumor, lymph node, metastasis roup will be collected.	
	Adverse events (AE) will be r with the Baseline visit.	nonitored at each visit, starting	
Planned trial dates	Start of study August 2015	End of Study June 2021	
Planned number of trial centers / countries	Up to 10 sites in the United St	ates	
Number of subjects	For the primary analysis of safety, at least 27 subjects administered Lymphoseek will be evaluated:		
	• At least 6 subjects with me	elanoma	
	• At least 6 subjects with rha	abdomyosarcoma	
	Enrollment will be open to up other tumor types in which biopsy (SLNB) are appropriate	to 15 additional subjects with ILM and sentinel lymph node e.	
	At least 20 of the recruited sub	pjects will be ≤ 16 years of age.	
Safety endpoints Primary	Incidence of AEs		
Secondary	Changes over time in vitals signs, laboratory tests, and ECGs		
Diagnostic endpoints	 Proportion of subjects lymph nodes (i.e., localization) 	with Lymphoseek-identified tion)	

	• Number of Lymphoseek-identified lymph nodes per subject (i.e., degree of localization)
	• Proportion of subjects who underwent preoperative SPECT lymphoscintigraphy
	• Comparison of the number of lymph nodes detected with Lymphoseek intraoperatively to the number of nodes detected with preoperative SPECT

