The localization rate, degree of localization, difference in preoperative SPECT versus intraoperative localization, agreement proportions of central pathology assessment to local pathology assessment, false negative rates, sensitivity rates, and upstaging, along with 95% confidence intervals, will be computed for each tracer (as applicable) for each tumor type and overall.
The proportion of ITT subjects with preoperative SPECT performed, those who had a hot spot on scan, and the time from Lymphoseek injection to hot spot localization, will be summarized by tumor type and overall.
Changes in nodal staging will be assessed via shift tables.
Changes in treatment plan and relation to lymph nodes will be listed.
Concordance endpoint analysis: For the BITT population, the number and proportion of concordant lymph nodes (Lymphoseek to Lymphazurin) will be computed, and a statistical test to determine if the concordance rate is greater than 0.9 will be conducted. In order for the test of the nodal concordance endpoint to successfully reject the null hypothesis that the concordance rate is ≤ 0.9 , the lower boundary of the one-sided 95% exact binomial confidence

interval must exceed 0.9 in the BITT population. In-house and/or literature data indicating that nodes may be considered as an independent sample will supplement the analysis.
If the test of the concordance endpoint is met (i.e., the null hypothesis is rejected), then a test for superiority of concordance relative to the secondary diagnostic endpoint of reverse concordance will be conducted using McNemar's test. If the one-sided p-value of the test is <0.05, then the concordance rate of Lymphoseek to Lymphazurin will be shown to be significantly greater than the reverse concordance rate of Lymphazurin to Lymphoseek.
The per-subject concordance and per-subject reverse concordance will also be computed along with 95% confidence intervals using the BITT population.
No formal interim analyses will be conducted during this study.
Data listings and tables will be created on an interim basis for review by a Data and Safety Monitoring Committee (DSMC), which is further described in Section 9.11.

TABLE OF CONTENTS

SY	NOPS	IS		2
LIS	ST OF	IN-TE2	XT TABLES	13
LIS	ST OF	APPEN	NDICES	13
LIS	ST OF	ABBR	EVIATIONS AND DEFINITIONS OF TERMS	14
TR	IAL A	DMIN	ISTRATIVE STRUCTURE	16
LA	BORA	ATORII	ES AND OTHER INSTITUTIONS FOR TRIAL CONDUCT	16
1	INT	RODU	CTION	17
	1.1	Back	ground	17

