9.6 Diagnostic Variables

9.6.1 Primary Diagnostic Variables

The primary diagnostic variables for this study are:

- Subject localization rate (defined as the proportion of subjects with Lymphoseekidentified lymph nodes)
- Number of lymph nodes identified intraoperatively by Lymphoseek per subject
- Proportion of subjects who underwent preoperative SPECT or SPECT/CT
- Proportion of subjects with a lymph nodes identified preoperatively using SPECT or SPECT/CT
- Number of lymph nodes identified preoperatively using SPECT or SPECT/CT
- Agreement of the number of nodes identified by preoperative SPECT or SPECT/CT to intraoperative localization
- Subject and nodal agreement of central pathology assessment with local pathology assessment of the excised lymph node(s) to confirm the presence/absence of tumor metastases
- Nodal false negative rate for Lymphoseek-identified nodes (using blinded central pathology assessment and local pathology assessment)
- Nodal sensitivity for Lymphoseek-identified nodes (using blinded central pathology assessment and local pathology assessment)
- Upstaging (defined as the proportion of patients with pathology-positive lymph nodes who had at least one pathology-positive lymph node that was identified by Lymphoseek and had no other pathology-positive lymph nodes [i.e., identified by any other method])
- Change in subject nodal staging before and after surgery based upon Lymphoseekidentified nodes
- Changes in treatment plan and relation to lymph nodes identified by Lymphoseek

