9.7 Sample Size Justification

Approximately 27 subjects will be enrolled into the study, at least 6 of whom have been diagnosed with melanoma and at least 6 of whom have been diagnosed with rhabdomyosarcoma. Enrollment will be open to up to 15 additional subjects with other tumor types in which ILM and sentinel lymph node biopsy (SLNB) are appropriate. At a minimum, 20 of the enrolled subjects will be ≤ 16 years of age and at least 25 subjects will complete the 4- to 14-day follow up. The sample size was chosen in order to provide a reasonable amount of data to assess the safety and diagnostic performance of Lymphoseek within this limited pediatric subject population.

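### SPECT-to-surgery count agreement is named as a variable in 9.6.1, but the mean signed difference planned in 9.9.5 estimates average bias, not per-subject agreement

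*Combined protocol and SAP*

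**What the plan says.** The protocol describes this item in three ways.

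- **Variable list (9.6.1).** Among the primary diagnostic variables: "Agreement of the number of nodes identified by preoperative SPECT or SPECT/CT to intraoperative localization".
- **Analysis (9.9.5).** The planned statistic begins "The average difference in the number of lymph nodes identified with preoperative SPECT per subject"; the other term of the difference is the intraoperative count per subject. A 95% interval is to accompany it, and the method for the interval is not given. The section also gives a separate mean for each count. It plans no proportion of subjects with equal counts, no distribution of the differences, no limits of agreement and no cross-tabulation.
- **Synopsis.** The diagnostic endpoint is "Comparison of the number of lymph nodes detected with Lymphoseek intraoperatively to the number of nodes detected with preoperative SPECT". The statistical plan there refers to "difference in preoperative SPECT versus intraoperative localization", with a 95% confidence interval. Neither place uses the word agreement for this item.

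Section 9.9.5 handles its other agreement variable differently. Central versus local pathology is analysed as a proportion whose numerator begins "Lymph nodes whose local and central pathology assessments were either" and counts matching results. A subject-level definition follows, and each proportion has a 95% interval.

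Lymphoscintigraphy is optional (synopsis; section 8.3). Section 9.8 restricts each endpoint to subjects with non-missing data. The number of subjects with both counts is therefore unknown in advance; planned enrolment is about 27 (9.7).

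**The concern.** A mean of signed differences answers one question: does SPECT find more or fewer nodes than surgery on average? Agreement is a different question: in how many subjects do the two counts match, and how far apart are they when they do not? Positive and negative differences cancel in the mean, so a value near zero is compatible with anything from complete agreement to none. The two separate means do not help, since their difference among subjects with both counts is the same quantity.

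At stake is whether the report will contain the quantity that 9.6.1 names. As planned, it will contain average bias and leave per-subject agreement unreported.

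**Working it through.** The protocol states no expected value, standard deviation, power or sample size for this variable, so there is no planned figure to reproduce. The check uses constructed counts.

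**Inputs and assumptions**
- d = SPECT count minus intraoperative count, per subject (9.9.5).
- n = 26 subjects with both counts. This is assumed; it is an even number just below the enrolment of about 27 in 9.7. Smaller n is shown below.
- A t interval, assumed because no method is stated.
- The patterns of d are invented to test the measure. They are not forecasts.

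**Formulas**
- When the mean of d is 0, SD = √(Σd² / (n − 1)).
- Half-width of the 95% interval = t(n − 1) × SD / √n.
- Exact agreement = number with d = 0, divided by n, with an exact binomial 95% interval.

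**Pattern A: no subject agrees.** 13 subjects at +1 and 13 at −1.
- Mean = (13 − 13)/26 = 0.00.
- SD = √(26/25) = 1.020; SE = 1.020/√26 = 0.200; t(25) = 2.060.
- Half-width = 2.060 × 0.200 = 0.41, so the interval is −0.41 to 0.41.
- Exact agreement = 0/26 = 0% (0 to 13.2%).

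**Pattern B: every subject agrees.** All 26 at 0.
- Mean = 0.00, SD = 0, interval of zero width.
- Exact agreement = 26/26 = 100% (86.8 to 100%).

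A and B have the same point estimate. Only the interval width separates them.

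**Pattern C: same mean and interval as A.** 3 subjects at +2, 3 at −2, 1 at +1, 1 at −1 and 18 at 0.
- Sum of d = 6 − 6 + 1 − 1 = 0, so the mean is 0.00.
- Σd² = 6 × 4 + 2 × 1 = 26, so SD = √(26/25) = 1.020 and the interval is again −0.41 to 0.41.
- Exact agreement = 18/26 = 69% (48.2 to 85.7%).

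| Pattern | Mean (95% interval) | Subjects with equal counts |
|---|---|---|
| A | 0.00 (−0.41 to 0.41) | 0/26 |
| B | 0.00 (0 to 0) | 26/26 |
| C | 0.00 (−0.41 to 0.41) | 18/26 |

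**Fewer imaged subjects.** With half at +1 and half at −1, n = 12 gives SD √(12/11) = 1.044 and half-width 2.201 × 1.044/√12 = 0.66. For n = 6, SD is √(6/5) = 1.095 and the half-width is 2.571 × 1.095/√6 = 1.15. The mean is 0.00 and agreement 0% in both. The width thus moves with n while agreement stays at zero.

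**The case against.** The strongest reply is that this is largely a matter of naming. Only the bullet in 9.6.1 says agreement. The synopsis endpoint and analysis, and the secondary objective on the number of nodes per subject by each method, are all served by a paired mean difference. That stands: the planned analysis suits those passages, and renaming the bullet would remove the contradiction. Renaming alone would still leave per-subject agreement unreported.

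A second reply is that the interval carries the spread. With n and a t interval, the SD can be recovered from the width, and full agreement would show as zero width. That stands in part. The width does separate patterns A and B, but not A and C, where the same mean and interval go with 0% and 69% agreement.

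Third, the protocol refers to a separate statistical analysis plan, which could add a measure. Those references concern further safety analyses (9.9.4) and the independence of nodes (9.9.6), not this variable. The absence can be asserted only for the text supplied.

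Fourth, equal counts do not show that the same nodes were found. This is correct, and it limits the proposed measure too. The proposal matches the variable as worded, which concerns the number of nodes.

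A reader might also infer that a mean near zero will be reported as SPECT agreeing with surgery. The documents do not support that: 9.9.5 says the difference and interval will be computed, and it sets no threshold, success criterion or interpretation.

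**Conclusion.** The mismatch between 9.6.1 and 9.9.5 is real and minor. The mean signed difference is a valid estimate of average bias and fits the synopsis, but it does not measure the agreement that 9.6.1 names. In the constructed cases it is 0.00 whether 0, 18 or 26 of 26 subjects agree. Those cases rest on invented differences, an assumed 26 paired subjects and an assumed t interval. They show what the measure can miss, not what this trial will find.

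The label primary diagnostic variable might suggest that a main trial conclusion is at risk. It is not. The primary objective is safety, and this is one of twelve items in 9.6.1, with no hypothesis and no sample size attached. It would also go too far to say that the plan cannot answer its question: it answers the synopsis question about the difference in counts and leaves the agreement question in 9.6.1 open.

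**What to change.** In section 9.9.5:

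1. Keep the mean difference and its 95% interval, label it as average bias, and state the interval method.
2. Add the proportion of imaged subjects whose SPECT and intraoperative counts are equal, with an exact 95% interval, and report the number of subjects with both counts.
3. Add a cross-tabulation of SPECT count by intraoperative count, so that the size and direction of disagreements can be seen.
4. State that equal counts do not show that the same nodes were found.

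Then align the wording of 9.6.1 and the synopsis, so that both name the difference (bias) and the agreement (equal counts) as separate quantities.

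The cost is one proportion, one table and a few lines of text. Both counts are already needed for the planned difference, so no new data, subjects or procedures are required.

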	• Comparison of centralized, blinded pathologic assessment to local pathologic assessment of the excised lymph node(s) to confirm the presence/absence of tumor metastases on a per-subject and per-node basis
	• False negative rates and sensitivity for each detection method in subjects undergoing lymphadenectomy
	• Upstaging
	• Change in nodal staging before and after surgery based upon Lymphoseek-identified nodes (and Lymphazurin, if applicable)
	• Number of changes in treatment plan and relation to lymph nodes identified by Lymphoseek
	Additionally for those subjects receiving both Lymphoseek and Lymphazurin:
	• Proportion of subjects with Lymphazurin-identified lymph nodes (i.e., localization)
	• Number of Lymphazurin-identified lymph nodes per subject (i.e., degree of localization)
	• Proportion of lymph nodes (and subjects) identified intraoperatively by Lymphazurin that are also identified intraoperatively by Lymphoseek (i.e., nodal and per-subject concordance)
	• Proportion of lymph nodes identified intraoperatively by Lymphoseek that are also identified intraoperatively by Lymphazurin control (i.e., nodal and per-subject reverse concordance)
	• Difference between nodal and reverse nodal concordance
Plan for statistical analysis	Analysis populations:
	• Safety: all enrolled subjects with administration of Lymphoseek
	• Intent-to-treat (ITT): all enrolled subjects with administration of Lymphoseek (with or without

Lymphazurin) and complete intraoperative lymphatic mapping
• Blue intent-to-treat (BITT): all ITT subjects with administration of Lymphazurin prior to ILM
• Per protocol (PP): all ITT subjects without major protocol violations
All safety analyses will be conducted on the safety population. The analysis of the diagnostic endpoints will be conducted on ITT, BITT, and PP populations, as applicable.
AEs will be summarized using system organ class and preferred term by tumor type and overall for all subjects in the safety population. AEs will also be summarized by severity, relationship to investigational product, and relationship to study procedure. All AEs will be listed.
Summary statistics (mean, median, sample size, standard deviation, minimum, and maximum) will be computed on the raw and change from baseline values for each vital sign parameter, quantitative laboratory parameter, and ECG parameter by time point, for each tumor type and overall.

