9.8 Handling of Missing Data

There will be no missing value imputation used in this study. All endpoints will be analyzed with subjects who have non-missing data (i.e., a complete case analysis).

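### Central-versus-local percent agreement does not show how many local positives were confirmed, and its missing-read rule can score a child positive on one read as agreed negative

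*Combined protocol and SAP*

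**What the plan says.** The Synopsis gives the purpose of the comparison as "to confirm the presence/absence of tumor metastases on a per-subject and per-node basis". Section 9.6.1 lists subject and nodal agreement among the primary diagnostic variables.

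Section 9.9.5 defines nodal agreement. Its numerator is "Lymph nodes whose local and central pathology assessments were either" "both positive or both negative", and its denominator is "Lymph nodes with non-missing local and central pathology results". A subject agrees if there is at least one positive node by local and central pathology, or if the subject "has all pathology-negative nodes with local and central pathology". For both levels, "only nodes that have non-missing local and central pathology results will be considered". Section 9.8 adds that "There will be no missing value imputation used in this study".

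Each proportion gets a 95% confidence interval and is also broken down by tumor type in the ITT and PP populations. Section 9.9.5 plans no split by positive or negative reading, no local-by-central table and no sensitivity analysis for missing reads. No hypothesis or threshold is attached to agreement.

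**The concern.** Presence and absence of metastasis are two questions, and the formula adds the two kinds of agreement together. Every child is clinically node negative at screening (section 4.1.1), so both-negative nodes may be the majority. The percentage can then be fairly high although few of the local positives were confirmed.

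The missing-read rule is a separate matter. Dropping a node that only one reader assessed also drops what that reader found. If the dropped node was the child's only positive one, the remaining negatives decide the child's status. The child is then misclassified within the agreement index, which is worse than a loss of precision.

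Some disagreement is to be expected. Local reading follows each institution's practice (section 8.5.1), while the central laboratory uses H&E and IHC (section 8.5.3). Missing central reads are possible because blocks or slides have to be shipped (section 8.5.2).

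**Working it through.** **The plan's own figure.** There is none to reproduce. Section 9.7 gives no target or expected value for agreement. The tumor-type numbers do add up: 6 + 6 + 15 = 27.

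**Inputs from the protocol (section 1.1).** Rhabdomyosarcoma: 81/592 = 13.7% (stated as 14%) in a surgical series and 6/28 = 21.4% in sentinel-node studies. Melanoma: 25.6% of children having sentinel-node biopsy. No rate is given for other tumors. Applied to 27 children:

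- 27 × 0.137 = 3.7, about 4
- 27 × 0.214 = 5.8, about 6
- 27 × 0.256 = 6.9, about 7

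**Assumptions.** 1 to 4 excised nodes per child (the documents give no figure), one positive node per positive child, every node read twice, and no positives found only centrally.

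**Formulas.** Let m be nodes per child, P the number of positive children and c the number of local positives confirmed centrally.

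- Nodal agreement = (27m − P + c) / 27m
- Subject agreement = (27 − P + c) / 27

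**None confirmed (c = 0), nodal agreement:**

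| Nodes per child | P = 4 | P = 6 | P = 7 |
|---|---|---|---|
| 1 | 23/27 = 85.2% | 21/27 = 77.8% | 20/27 = 74.1% |
| 2 | 50/54 = 92.6% | 48/54 = 88.9% | 47/54 = 87.0% |
| 3 | 77/81 = 95.1% | 75/81 = 92.6% | 74/81 = 91.4% |
| 4 | 104/108 = 96.3% | 102/108 = 94.4% | 101/108 = 93.5% |

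Subject agreement equals the first row whatever m is: 74.1% to 85.2%.

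**About half confirmed** (2 of 4, 3 of 6, 4 of 7). Nodal agreement runs from 24/27 = 88.9% to 106/108 = 98.1%. With P = 6 and 2 nodes per child it is 51/54 = 94.4% (exact 95% CI 84.6-98.8%, treating nodes as independent), while confirmation of local positives is 3/6 = 50% (CI 12-88%).

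**Missing-read rule, followed literally.** A child has node A, locally positive with no central result, and node B, negative on both reads. Node A is dropped, only node B remains, and the child is scored as agreed negative. The same happens if node A is centrally positive with no local result. At least one other double-negative node is needed; without any paired node there is nothing to compare.

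Illustration with 27 children, 6 of them locally positive. Two of the six are in the situation above, the other four are confirmed, and the 21 negative children agree:

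- rule as written: 27/27 = 100% (CI 87.2-100%)
- the two children excluded as undetermined: 25/25 = 100% (CI 86.3-100%)
- the two children counted as not agreed: 25/27 = 92.6% (CI 75.7-99.1%)

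In the extreme, if all six are in that situation, the rule still gives 27/27 although no positive reading was ever compared.

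**The case against.** A reader might infer that the plan offers a single percentage that stays high whatever happens to the positive nodes, and so cannot confirm metastases. The documents do not support that.

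- Agreement is given per node and per subject, overall and by tumor type, with confidence intervals. Total failure to confirm would show as 74-85% at subject level, and the same at node level with one node per child. Neither figure is reassuring.
- A node positive on both reads is a confirmed metastasis.
- Sections 9.9.5 and 9.9.6 compute sensitivity and false negative rate separately under central and local pathology, so each reader's total of positive nodes should be visible. If every node has both reads and all outputs use the same nodes, those totals and the agreement figure fix the 2x2 table: both-positive = (local positives + central positives − discordant) / 2. In the 51/54 example this is (6 + 3 − 3)/2 = 3.

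These points stand, with limits. The identity fails once reads are missing, which is exactly when the second problem arises. The Synopsis also ties false negative rate and sensitivity to subjects undergoing lymphadenectomy, so the node sets may differ. Sensitivity and false negative rate describe the tracer and do not cross-classify the two readers. A reader should not have to rebuild the table by algebra.

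Two further points are fair. Agreement is descriptive and the primary objective is safety. And sections 9.9.4 and 9.9.6 refer to a statistical analysis plan whose separate text is not in the document, so a 2x2 table there cannot be excluded. The section 9.9.5 rule would still misclassify the child.

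**Conclusion.** The point holds in limited form. Overall percent agreement alone does not show how many local positives were centrally confirmed. How far it hides this depends on nodes per child, which the documents do not give: strongly at 3 or 4, weakly at 1. The ranges also rest on applying tumor-specific positivity to all 27 children and on central review adding no positives.

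The missing-read rule follows directly from the wording of section 9.9.5 and needs no numerical assumption, but its frequency cannot be estimated. A reader might infer that a node-positive child would be treated as negative throughout the analysis. The documents do not say so: the both-reads rule is stated only for nodal and subject agreement, and does not alter staging, sensitivity or false negative rate.

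The change should be made, but nothing here threatens the primary safety objective.

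**What to change.** In section 9.9.5:

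- Report the local-by-central 2x2 table at node and at subject level. Give positive agreement (share of local positives confirmed centrally) and negative agreement (share of local negatives read negative centrally), each with a 95% confidence interval. Node-level intervals should allow for clustering by child.
- Keep overall percent agreement as a supplement.
- Class a child as not evaluable for subject agreement when a node positive on one read lacks the other read and no other node is positive on both. Report the number of such children, with a bounding analysis that counts them as not agreed.

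The cost is wording and table programming on data already collected. The downside is a wide interval for positive agreement: 3/7 gives 10-82%, and even 7/7 gives 59-100%. That width reflects how little information 4 to 7 expected positive children can provide.
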